2.2 Analysis sets

The **Intent to Treat Analysis Set (ITT)** comprises all randomized participants, regardless of whether they were dosed with study treatment during Treatment Period 1. Participants will be analyzed according to the treatment/procedure they have been assigned to.

The **Full Analysis Set (FAS)** comprises all randomized participants who were dosed with study treatment during Treatment Period 1. Participants will be analyzed according to the treatment/procedure they have been assigned to.

As per the protocol, participant randomization occurs approximately 2 weeks prior to when treatment administration/sham procedure is planned to occur. There is a possibility that a participant is randomized but subsequently becomes ineligible for the trial during this time and ultimately would not be dosed with the study treatment or contribute to the post-treatment study assessments. In order to account for this possibility, the FAS will exclude participants who were randomized but were not dosed with the study treatment.

The **Active Treatment Period 2 Set (ATP2)** comprises all participants who were dosed with the study treatment during Treatment Period 2. Summaries of data using ATP2 will be based on actual treatment/treatment sequence.

The **OAV101 Treated Analysis Set (OAS)** comprises all randomized participants who were dosed with OAV101 treatment during Treatment Period 1 or 2. Participants will be analyzed according to the treatment/procedure they have been assigned to.

The **Safety Analysis Set (SAF)** includes all participants who were dosed with the study treatment during Treatment Period 1. Participants will be analyzed according to the study treatment/procedure received.

2.2.1 Subgroup of interest

Age at the time of informed consent, grouped as ≥ 2 to < 5 years and ≥ 5 to < 18 years, is considered to be the subgroup of interest for this SAP.

The following analyses will be rerun using the subgroup of participants in China and India separately.

Type of Analysis	Analysis Set
Disposition (by age group and overall)	ITT and ATP2
Demographics, baseline characteristics and SMA medical history (by age group and overall)	ITT
Previous SMA diagnosis at period 1 (by age group and overall)	ITT
Confirmatory genetic testing at period 1 (by age group and overall)	ITT
Analysis sets (by age group and overall)	ITT, ATP2
Relevant medical histories and current medical conditions (by age group and overall)	ITT
Prior medications	ITT
Protocol deviations (by age group and overall)	ITT
Primary endpoint analyses	FAS
Secondary endpoint analyses	FAS
Concomitant medications	SAF
Study treatment exposure by age group	SAF
Prophylactic prednisolone exposure	SAF
Laboratory data	SAF
CCI	[REDACTED]
Adverse Event data	SAF

2.3 Patient disposition, demographics and other baseline characteristics

2.3.1 Patient disposition

Disposition will be presented for all participants, and will include the following summaries:

- The number and percentage of participants who were screened and who subsequently failed screening, along with the reasons for screen failure will be summarized.
- The number and percentage of participants randomized and included in each analysis set (ITT, FAS, ATP2, OAS, SAF). Percentages will be based on the number of randomized participants.
- The number and percentage of participants in the ITT who:
 - Completed Follow-up Period 1, defined as all participants with a Week 52 visit conducted either remotely or at the study site
 - Discontinued prior to the end of Follow-up Period 1 and the associated reason for discontinuation
 - Completed Follow-up Period 1 and continued to Treatment Period 2
 - Completed Follow-up Period 1 and did not enter Treatment Period 2 and the associated reason for not entering Treatment Period 2

The above summary will be produced by Treatment Period 1 treatment group (OAV101, sham) and overall, and separately broken out by age subgroup (≥ 2 to < 5 years, ≥ 5 to < 18 years) within each treatment group.

- The number and percentage of participants in the ATP2 who:
 - Completed Follow-up Period 2, defined as all participants with a Week 64 visit conducted either remotely or at the study site
 - Discontinued prior to the end of Follow-up Period 2 and the associated reasons for discontinuation

The above summary will be produced by treatment sequence across Treatment Periods 1 and 2 (OAV101/sham, sham/OAV101) and overall, and separately broken out by age subgroup (≥ 2 to < 5 years, ≥ 5 to < 18 years) within each treatment sequence.

A listing of participant disposition will be produced.

2.3.2 Demographics and other baseline characteristics

The age of the participant at the time of the screening visit 1 will be summarized using descriptive statistics. The participant's age will be collected on the CRF in terms of both years and months (i.e. a participant's age may be recorded as 5 years, 2 months old). Age in years will be derived for each participant as follows.

- Age (years) at screening visit 1 = [(recorded years * 12) + (recorded months)] / 12
- Age (days) at screening visit 1 = (recorded years * 365.25) + (recorded months * 30.4375)

- Age (years) at dosing on day 1 = [Age (days) at screening visit 1 + (Day 1 visit date – Screening 1 visit date)] / 365.25

The following demographic and baseline characteristics will be summarized by treatment Period 1 treatment group (OAV101, sham) and overall, and separately broken out by age subgroup (≥ 2 to < 5 years, ≥ 5 to < 18 years) within each treatment group for the ITT and FAS:

- Age (years) at screening visit 1
- Age (years) at dosing on day 1
- Sex
- Race
- Ethnicity
- Randomization strata assignment (combination of age and HFMSE score at Screening)
- SMN2 copy number (study specific genetic reconfirmation)
- Number of patients with 1 vs 0 SMN1 copy number
- Country

If a participant reports multiple races, they will be categorized as “multiple races” in the summary table.

A listing of genetic testing parameters will be provided .

2.3.3 Medical history

The presence of significant medical conditions obtained at study entry will be summarized by Medical Dictionary for Regulatory Activities (MedDRA) System Organ Class (SOC) and Preferred Term (PT). The dictionary version used will be noted in the summary tables and listings. Summaries will be produced by age subgroup (≥ 2 to < 5 years, ≥ 5 to < 18 years) within each Treatment Period 1 treatment group (OAV101, sham) and overall for the ITT.

The following parameters will be summarized regarding symptoms and history of SMA:

- Familial history of SMA, including parent carriers and affected sibling(s)
- SMA diagnosis method
- Presence/absence of bi-allelic deletion, point mutations, and genetic modifier G>C.859
- Survival Motor Neuron 2 gene (SMN2) copy number
- Age at SMA symptom onset
- Highest motor function achieved
- Number of hospitalizations for pneumonia with/without respiratory failure
- Current SMA symptoms
- Total time observed sitting independently at Screening (seconds)

Symptoms and history of SMA will be summarized by age subgroup (≥ 2 to < 5 years, ≥ 5 to < 18 years) within each Treatment Period 1 treatment group (OAV101, sham) and overall for the ITT and FAS.

SMA Medical history and diagnosis will be listed. Additionally, a listing of the Scoliosis assessment conducted at Screening will be produced.

2.3.4 Protocol deviations

All protocol deviations (PDs) will be recorded in the clinical database and will be categorized in accordance with Novartis SOPs. PDs through the end of Follow-up Period 1 will be summarized by PD coded term and treatment group by age group and overall using the ITT set. A listing of all PDs occurring through the end of the study will also be created. A separate listing will be produced to summarize all important PDs occurring through the end of the study.

2.4 Treatments (study treatment, rescue medication, concomitant therapies, compliance)

2.4.1 Study treatment / compliance

The following details pertaining to treatment administration will be summarized using descriptive statistics by age subgroup (≥ 2 to < 5 years, ≥ 5 to < 18 years) and overall (≥ 2 to < 18 years). Separate summary tables will be produced for Treatment Period 1 using the SAF and for Treatment Period 2 using the ATP2 population:

- Anatomical location of administration (L2-L3, L3-L4, L4-L5, L5-S1)
- Number and percentage of participants taking prednisolone/placebo 24 hours prior to injection
- Number and percentage of participants with dose interruption and their corresponding reason
- Treatment compliance (%) if the dose is not fully completed. Treatment compliance is defined as 100 times the dose administered divided by the planned dose. Planned dose is 3ml, equivalent to 1.2×10^{14} vector genomes.

A listing of treatment administration during both Treatment Periods will be produced.

2.4.2 Prior, concomitant and post therapies

Prior and concomitant medications and significant non-drug therapies taken prior to and after the start of the study treatment will be listed and summarized according to the World Health Organization Drug Dictionary (WHODD) Anatomical Therapeutic Chemical (ATC) classification system. The dictionary version used will be noted in the summary tables and listings.

A prior medication is defined as any medication taken prior to the date of the administration of study treatment during Treatment Period 1. A concomitant medication is defined as any medication that started prior to the date of the administration of study treatment during Treatment Period 1 and continued to be taken after the administration of study treatment during Treatment Period 1 or any medication that started on or after the date of the administration of study treatment during Treatment Period 1. With this approach, a medication may be classified as both prior and concomitant.

The number and percentage of participants taking prior medications in the ITT and concomitant medications in the SAF through the end of Follow-up Period 1 will be summarized by ATC2 and generic drug name based on the WHODD by overall.

A second summary will be produced to detail the concomitant medications initiated after dosing with OAV101 through the end of Follow-up Period 2. This summary will combine all concomitant medications taken by participants who were treated with OAV101 during Treatment Period 1 or 2. For participants who underwent the sham administration procedure during Treatment Period 1 and received OAV101 during Treatment Period 2, only medications initiated after dosing during Treatment Period 2 will be included.

Listings will be produced to summarize the prior and concomitant medications taken throughout the study. The listing of concomitant medications will include all medications taken through the end of Follow-up Period 2.

2.4.2.1 Specific medication subgroups

To reduce the host immune response to the adeno-associated virus (AAV)-based therapy, all participants randomized to the OAV101 treatment arm will receive CCI

CCI

CCI

2.5 Analysis supporting primary objective(s)

The primary analysis will be performed after all participants have completed Week 52 or discontinued prior to Week 52. A final analysis will be performed after all participants have completed Week 64 or discontinued prior to Week 64. Formal testing of the primary endpoint with full alpha level will be performed at the primary analysis time point.

2.5.1 Primary endpoint

The primary endpoint of the study is the change from Baseline in HFMSE total score at the end of Follow-up Period 1 in the ≥ 2 to < 18 year age group.

2.5.2 Statistical hypothesis, model, and method of analysis

The aim is to estimate the treatment effect of IT OAV101 compared to the sham procedure, for the target population on the primary endpoint. The justification of the corresponding primary estimand is detailed in [Section 1.2.1](#) of this SAP.

The statistical hypothesis for the primary endpoint being tested is that there is no difference in the change from Baseline in HFMSE total score at the end of Follow-up Period 1 in the OAV101 treatment group compared to the sham procedure group.

Let p_j denote the change from Baseline in HFMSE total score at the end of Follow-up Period 1 for treatments j , $j=0, 1$ where:

- 0 corresponds to sham procedure
- 1 corresponds to OAV101

In statistical terms, $H_0: p_1=p_0$, $H_A: p_1 \neq p_0$, i.e.:

- H_0 : OAV101 is not different from sham procedure with respect to the change from Baseline in HFMSE total score at the end of Follow-up Period 1.
- H_A : OAV101 is different from sham procedure with respect to the change from Baseline in HFMSE total score at the end of Follow-up Period 1.

The primary efficacy endpoint variable will be analyzed using a linear mixed effects repeated measures model (MMRM) with the observed change from Baseline in HFMSE total score at all post-Baseline visits (through the end of Follow-up Period 1) as the dependent variable. The fixed effects will include treatment, scheduled visit, treatment by visit interaction, CCI [REDACTED]

[REDACTED]. The primary analysis will be based on the FAS. An unstructured covariance matrix will be used. LSMs for each treatment group, standard errors, and associated 95% confidence intervals (CIs), difference of LSMs compared to sham procedure group, and the associated 95% CI for the difference, as well as the two-sided p-values will be tabulated by visit. The null hypothesis will be rejected if the two-sided p-value for the LSM difference between the OAV101 arm and the sham procedure at the end of Follow-up Period 1 is less than the alpha level dictated by the sequential testing procedure ([Figure 2-1](#)).

A line plot will be produced to display the LSMs for each treatment group and associated 95% CIs at each visit through the end of Follow-up Period 1.

In case of non-convergence issues, the covariance matrix will be simplified and a compound symmetry (CS) matrix will be used instead of the originally planned unstructured covariance matrix.

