- **RULM**: Baseline value for RULM total score is defined as the average of all non-missing assessments prior to the first administration of study treatment during Treatment Period 1, assuming all assessments have complete and valid total scores available. If two of the assessments have a complete and valid total score available, then the baseline RULM total score is defined as average of the two available assessment scores. If just one of the assessments has a complete and valid total score available, then the baseline RULM total score is defined as the single total score available.
- **Other assessments**: The latest non-missing measurement or evaluation made prior to the first administration of study treatment during Treatment Period 1.

Change from baseline is defined as post-baseline value minus baseline value.

For HFMSE and RULM, the **End of Follow-up Period 1** assessment is defined as the average of the Week 48 and Week 52 assessments, assuming both assessments have complete and valid total / individual scores available. If just one of the assessments collected at these two visits has a complete and valid total / individual score available, then the end of Follow-up Period 1

assessment is defined as the single assessment total / individual score collected at Week 48 or Week 52.

Last participation day can be calculated using end of participation date – date of second administration of study treatment + 1.

Inexact values will be handled as follows.

- If a laboratory value is recorded/reported as “>X”, “≥X”, “- If an antibody titer value is reported as <12.5, a value of 0.5×12.5 will be used and if ≥ 819200 is reported, a value of 1.5×819200 will be used for analysis purposes. The originally recorded values will be displayed in corresponding listings.

An **Adverse Event** (AE) is any untoward medical occurrence in a clinical investigation participant, which does not necessarily have a causal relationship with the drug or device under study.

A Treatment Emergent Adverse Event (TEAE) is any AE whose onset or worsening occurred after dosing on Day 1 till the end of follow-up period 2.

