2.13 Interim analysis

No formal interim analysis is planned for this trial.

3 Sample size calculation

The sample size calculation is primarily based on the primary variable, change from Baseline in HFMSE total score.

CCI [REDACTED]

[REDACTED]

[REDACTED]

CCI

Assuming a true treatment difference in the change from Baseline in HFMSE of 3 points and a standard deviation of 5 points, a sample size of 125 participants (75 in the OAV101 treatment group and 50 in the sham procedure group) provides approximately 90% power that the primary analysis will be statistically significant at the two-sided 5% alpha level assuming a minimal number of participants prematurely withdraw from the study prior to Week 52. In addition, assuming a larger treatment difference in the change from Baseline in HFMSE total score of 5 points and the same standard deviation as anticipated in the overall study population (5 points) in the ≥ 2 to < 5 years old group, a sample size of 65 participants (39 in the OAV101 treatment group and 26 in the sham procedure group) could achieve $> 95\%$ power in this younger age group.

Because this is the first OAV101 clinical trial to include the RULM assessment, there are no historical data available upon which to base sample size calculations on.

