5.1.4.1 Multiple imputation sensitivity analysis steps

The following steps will be followed, in order to create the structure of the analysis dataset where missing values and appropriate variables could be imputed.

- Obtain participant ID (USUBJID), treatment group (TRT01PN), and stratification factor from ADSL (subject level analysis dataset)
- Obtain visit (AVISITN), parameter code (PARAMCD), parameter (PARAM), numeric score value (AVAL), character score value (AVALC), baseline value (BASE), change from baseline value (CHG), and derivation type (DTYPE) from the applicable efficacy dataset
- Transpose all data so the dataset takes the format of one observation per participant, and each visit becomes a variable within its own right, e.g. rows where AVISITN=2004, 2008, 2012 become the columns WK4, WK8, WK12, etc.
- Impute the missing data for MAR and MNAR separately according to the methods in next steps.

MAR multiple imputation steps:

Note that there will be a mix of categorical and continuous variables in the modelling of the missing data. Therefore, fully conditional specification (FCS) methods are employed within PROC MI to impute the missing data.

- FCS logistic is used for dichotomous variables; DISCRIM is used for categorical variables with more than 2 categories; REGPMM is used for continuous variables.
- WK0, WK4, WK8, WK12, WK16, WK20, WK24, WK28, WK32, WK36, WK40, WK44, W48, and W52 represent the AVAL variables for each of the visits respectively, where WK0 is baseline.
- Compute the average of values at WK48 and WK52 to create a virtual AVISITN for End of Follow-up Period 1 for the average for each subject and each imputation, and then add to the total dataset.

MNAR multiple imputations steps:

- Here is an implementation of the pattern-mixture model approach that uses a tipping-point-based pattern of imputation, assuming systematically worse results than what's been imputed in the MAR MI analysis.
- For this purpose, a delta-adjustment approach will be followed, whereby a systematic shift will be added to all imputed values of the total HFMSE (or RULM) score for the OAV101 treatment group, and no shift will be added to the sham administration arm, to estimate the treatment effect in a conservative scenario.
- The choice of these delta values will be based on clinical/practical judgement to reflect plausible difference that could have occurred.

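### Compound symmetry is the only fallback for the primary MMRM and can misstate the standard error; name fallbacks with visit-specific variances, and state the visit levels

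*SAP*

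**What the plan says.** - **Model.** SAP 2.5.2 takes as dependent variable the "observed change from Baseline in HFMSE total score at all post-Baseline visits (through the end of Follow-up Period 1", with an unstructured covariance matrix. The hypothesis test is the LS mean difference at the end of Follow-up Period 1.
- **Fallback.** The same section says that, on non-convergence, "a compound symmetry (CS) matrix will be used instead of the originally planned unstructured covariance matrix". It names no other step.
- **Tested time point.** In SAP 2.1.1 the end of Follow-up Period 1 "assessment is defined as the average of the Week 48 and Week 52 assessments", or the single score if only one is available. The data analysis row of the protocol summary likewise says the two scores are averaged to form this time point.
- **Visits.** SAP 2.1.2 lists 13 post-baseline HFMSE/RULM visits, every 4 weeks from Week 4 to Week 52. Week 48 (Days 324 to 351) and Week 52 (from Day 352) have separate windows.
- **Multiple imputation.** SAP 5.1.4.1 says "Compute the average of values at WK48 and WK52 to create a virtual AVISITN for End of Follow-up Period 1" and adds the result to the dataset. The model fitted there is an ANCOVA.
- **Secondaries.** SAP 2.6.2 analyses the continuous HFMSE and RULM endpoints in a similar manner to the primary, including those for the group aged 2 to under 5 years.
- **Variability.** SAP Section 3 gives one figure: "Assuming a true treatment difference in the change from Baseline in HFMSE of 3 points and a standard deviation of 5 points".

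**The concern.** Under CS, the standard error at any one visit comes from a variance pooled over all visits. If change scores spread out over the year, early visits have small variances and the tested time point a large one. Pooling then makes the standard error at the tested time point too small and the p-value too optimistic. If the variance is constant, the pooling does no harm. The rule therefore moves from a structure that makes no assumption about variances to one that makes the strongest, with nothing in between.

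How often the fallback would be needed depends partly on something the visible text leaves open: which visits are levels of the model. The number of levels sets the number of covariance parameters. One possible layout cannot be fitted with an unstructured matrix at all. At stake are the primary test and the continuous secondaries. In the younger group, about 65 children would have to support 78 or more covariance parameters.

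**Working it through.** **Inputs from the documents.** Two-sided alpha 5%; difference 3 points; SD 5 points; arms of 75 and 50 (SAP Section 3); 13 scheduled visits (SAP 2.1.2). **Assumption:** the pattern of variance by visit, which the documents do not give. All patterns below are scaled to SD 5 at the end of Follow-up Period 1.

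**1. The plan's own figure.** The plan states that the sample "provides approximately 90% power".
- SE = 5 × √(1/75 + 1/50) = 0.913
- Power = Φ(3/0.913 − 1.96) = Φ(1.326) = 90.8% (90.3% with the t distribution)

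The stated power reproduces.

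**2. Rank of the unstructured matrix.** With m levels there are m(m+1)/2 parameters.

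| Layout | Levels | Parameters | Rank |
|---|---|---|---|
| Average replaces Weeks 48 and 52 | 12 | 78 | 12 |
| 13 visits, average taken as a contrast | 13 | 91 | 13 |
| 13 visits plus the average | 14 | 105 | 13 |

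In the third layout, ½ Week 48 + ½ Week 52 − average is zero for everyone with both scores, so one direction has no variance. The single-score rule does not rescue it. One dataset of 125 was simulated with 4 missing Week 52, 3 missing Week 48 and 4 missing both. The maximum-likelihood fit (EM algorithm) saw its log-likelihood climb without settling (−4623 to −1976) and lost positive definiteness at iteration 16. On the same data the 12- and 13-level fits converged.

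**3. Standard error under CS.** With balanced data and the average as a level:
- CS SE / true SE = √(mean of the level variances / variance of the average)
- Type I error = 2 × [1 − Φ(1.96 × ratio)]

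Worked example with 12 levels: the variance at visit k is proportional to 0.8(k/13)² + 0.2, that is, a random slope plus independent error.
- Sum over Weeks 4 to 44: 0.8 × 506/169 + 11 × 0.2 = 4.595
- Variance of the average: 0.8 × (12.5/13)² + 0.2/2 = 0.840
- Mean over 12 levels: (4.595 + 0.840)/12 = 0.453
- Ratio: √(0.453/0.840) = 0.734, so CS reports 0.67 where the true SE is 0.913
- Type I error: 2 × [1 − Φ(1.439)] = 0.150

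The other patterns follow in the same way. Each was checked with 10,000 simulated null trials. Cells show SE ratio; type I error by formula; type I error simulated.

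| Pattern (t = k/13) | SD at Week 4 | 14 levels | 12 levels |
|---|---|---|---|
| Constant variance, correlation 0.7 | 5.42 | 1.079; 0.034; 0.029 | 1.078; 0.035; 0.029 |
| Constant variance, AR(1) 0.95 | 5.06 | 1.012; 0.047; 0.046 | 1.012; 0.047; 0.046 |
| Random walk 0.7 + error 0.3 | 3.31 | 0.921; 0.071; 0.067 | 0.888; 0.082; 0.078 |
| Slope 0.6 + error 0.4 | 3.66 | 0.916; 0.073; 0.067 | 0.876; 0.086; 0.082 |
| Intercept 0.3 + slope 0.5 + error 0.2 | 3.82 | 0.900; 0.078; 0.077 | 0.872; 0.088; 0.085 |
| Slope 0.8 + error 0.2 | 2.47 | 0.789; 0.122; 0.114 | 0.734; 0.150; 0.143 |
| Pure random walk | 1.43 | 0.776; 0.128; 0.129 | 0.730; 0.153; 0.152 |

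Under constant variance the test is slightly conservative because an average of two visits varies less than a single visit. The unstructured 12-level analysis kept type I error between 0.045 and 0.051 throughout.

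**Limits.** The type I error simulations used complete data and no covariates, and the fit in step 2 used ML rather than REML. The sizes in step 3 apply where the average is itself a level; CS with the 13-visit contrast was not sized.

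**The case against.** A reader might infer more: that Week 48, Week 52 and their average all enter the model as written, so the primary analysis is bound to fail and drop to CS. The documents do not support that.

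- SAP 2.5.2 does not list the visit levels. The protocol summary fits the average serving as the last level. The model's visit effect is described as scheduled visit, which fits 13 visits with a contrast. Both layouts are full rank.
- The instruction to add the average to the dataset belongs to the multiple-imputation steps, which run only if more than 5% of participants lack the endpoint and then use ANCOVA. It does not define the MMRM's levels.
- Separate windows for Weeks 48 and 52 are needed anyway, to compute the average and for by-visit summaries.
- Part of the model sentence in SAP 2.5.2 and the estimand's endpoint bullet are blacked out, and the text of protocol Section 12.4 is not available here. The answer may be there.

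It can also be said that the direction of the CS error is not fixed. No SD by visit is given, and under constant variance CS is harmless. Protocol 4.5.2 reports that over 12 months 62% of untreated sitters were stable, 25% lost and 13% gained more than 2 points. That makes diverging courses plausible, but it does not give a variance by visit.

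These objections stand against the stronger reading. They leave untouched the fallback rule, which is stated outright, and the missing list of visit levels. The CS weakness does not depend on the singularity: it applies to any failed fit, and in the growing-variance patterns it is somewhat worse with 12 levels than with 14.

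**Conclusion.** The concern holds as a weakness in a stated rule. If the unstructured model fails, the SAP's sole fallback gives a type I error of about 3% to 5% under constant variance and about 7% to 15% under variance that grows with time, against a nominal 5%. The standard error runs from about 8% too large to about 27% too small. This range rests on assumed variance patterns, complete data and no covariates.

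The documents do not show that the fallback will be used, nor that the standard error would be far too small. Singularity follows only if the average is added as a fourteenth level, which is one possible reading of an incomplete specification. The younger-group secondaries share the rule and have fewer participants to support the same matrix.

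**What to change.** Two edits to SAP 2.5.2, carried into 2.6.2 for the continuous secondaries:

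1. **Ordered fallback.** Replace the single CS step with a fixed sequence: unstructured; heterogeneous Toeplitz; heterogeneous AR(1); heterogeneous CS; and only then homogeneous CS with a robust (sandwich) standard error. Use the first that converges. With 12 levels, heterogeneous Toeplitz needs 12 variances + 11 correlations = 23 parameters, and heterogeneous AR(1) or CS needs 12 + 1 = 13, against 78 for unstructured.
2. **Visit levels.** State one of two layouts. Either Weeks 4 to 44 plus the end of Follow-up Period 1 (12 levels), with Weeks 48 and 52 entering only through their average; or all 13 visits, testing the equal-weight contrast of Weeks 48 and 52. The second keeps by-visit LS means for Weeks 48 and 52 in the same model. If the redacted text already settles this, a cross-reference is enough.

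The cost is a slightly longer specification and no new data. The design power calculation is unaffected. The sandwich standard error needs a small-sample correction, above all in the group of about 65, and it does not correct any bias in the estimate that a wrong covariance can cause when data are missing.
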